Figure 1: A summary of the audiometric and speech eligibility criteria to distinguish the categories of patients who are eligible for the COACH trial (yellow areas; RCT: Randomised Controlled Trial) from those who are currently eligible under NICE guidance (grey area).

PRIMARY OBJECTIVE

To evaluate the effect of cochlear implantation on speech understanding in quiet in comparison to the use of acoustic HAs in adults with severe hearing loss whose audiometric thresholds and/or speech perception scores fall outside current UK candidacy criteria for cochlear implantation (as per NICE guidance TA566).

SECONDARY OBJECTIVES

- a. To evaluate the effect of cochlear implantation on broader hearing-related outcomes including speech understanding in noise, difficulties with listening in everyday environments, listening-related fatigue, and tinnitus in comparison to those using acoustic HAs.
- b. To evaluate the effect of cochlear implantation on broader health and well-being outcomes including mood, hearing-related quality of life, and health-related quality of life in comparison to those using acoustic HAs.
- c. To assess the safety of cochlear implantation and acoustic HAs.
- d. To characterise the duration and nature of CI and HA use.

TRIAL DESIGN

TRIAL CONFIGURATION

The trial will be a two-arm, multi-centre, parallel group, open, randomised controlled trial of CIs versus HAs.

Participants will be randomised to one of two treatment groups:

Intervention: Unilateral cochlear implantation and offer of a new acoustic HA or optimisation of current HA in the contralateral ear.

Comparator: Offer of new bilateral acoustic HAs or optimisation of current HAs.

Participants will be followed up at 1, 3, 6 and 9-months post treatment activation (T0). The primary outcome will be collected at the 9-month timepoint as clinicians report that the identification of words following cochlear implantation stabilises between approximately 3-6 months and therefore assessment at 9 months will ensure performance has reached asymptote.

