There is no planned interim analysis of treatment efficacy and no formal stopping rules. The Data Monitoring Committee (DMC) and Trial Steering Committee (TSC) will have ongoing oversight of the safety and feasibility of delivery of the trial. The DMC will also review data to ensure the trial has sufficient power to detect a clinically important difference between the two groups.

Randomisation and Blinding

Before randomisation can take place, a series of eligibility assessments need to take place to ensure the potential participant is suitable for all trial interventions. Consent is received prior to eligibility assessment and reconfirmed prior to randomisation. Randomisation cannot take place until a CI surgeon with delegated responsibility has confirmed the potential participant is eligible, following agreement from the MDT.

Randomisation

After reconfirmation of consent and recording of baseline measures, randomisation will take place at the trial site.

Participants will be assigned to treatment groups in a 1:1 ratio, using a concealed, secure internet-based randomisation system developed and maintained by the NCTU. The system will use a minimisation algorithm including a random component, with the following variables and levels: participating site; severity of tinnitus (Tinnitus Functional Index (TFI) score mild (0-28), moderate - significant problems (29-65), and severe (≥ 66)); AB word test phoneme score at 70 dBA $< 50\%$ and $\geq 50\%$. Participants that report no tinnitus will be given a score of 0 which falls under 'mild' tinnitus within the TFI. Access to the randomisation system will be granted to site staff by the NCTU in accordance with the roles delegated by the local Principal Investigator (PI) as documented on the delegation log.

Following randomisation, the participant's GP will also be informed that the participant is taking part in the trial by post.

Blinding

Participants, clinicians and treating staff cannot be blinded to the treatment allocation due to the requirement for some participants to undergo a surgical procedure to receive a CI and the obvious visible differences between a CI speech processor and a HA. However, to minimise bias, the baseline and 9-month measures of the primary outcome will also be video recorded and scored by two independent blinded assessors whose score will be that used in the primary outcome analysis.

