- Patient characteristics falling outside the indications for use of the trial devices as per their CE marking
- Inability to undergo speech perception testing and/or inability of audiologist to obtain an accurate measurement of speech perception abilities
- Patients who would not be able to adhere to trial procedures or complete the trial questionnaires
- Patients whose hearing loss is suspected or confirmed to be wholly or partly unexplained by anatomic or physiologic abnormalities (non-organic hearing loss)
- Patients who have a congenital profound hearing loss (no measurable or aidable hearing in both ears from birth)
- Any known factor that may restrict full insertion of the electrode array
- Patients with any known contraindication for cochlear implantation
- Patients whose primary concern is the suppression of tinnitus
- Patients in whom cochlear implantation would present an unacceptable risk to balance function
- Any serious concerns about medical fitness for surgery or cochlear implantation
- Participation in other research related to hearing loss while participating in the trial (i.e., until collection of the primary outcome), including research that involves any changes to or use of hearing devices, changes to hearing care/management, or duplication of trial outcome assessments

It is possible that a participant's hearing loss may progress to the extent that cochlear implantation would be recommended as per NICE Guidance TA566. If this arises before they have been randomised in the trial, the participant would become ineligible for trial participation and would be free to access CI services on the NHS. The participant would not be randomised as they would not meet eligibility criteria at the point of randomisation. If this situation arises after randomisation, the participant would remain in the trial for as long as they had not withdrawn their consent. If it is found that a participant has become eligible for a CI on the NHS at any stage of their participation in the trial, they will be informed of this.

All efforts will be made to continue follow up procedures and further treatment details would be collected (for example, if a participant had a CI procedure prior to the end of the 9 month period post treatment activation).

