4. disease or disorder being studied, or sign or symptom associated with the disease or disorder unless more severe than expected for the participant's condition.
5. overdose of concurrent medication without any signs or symptoms.
6. expected AE as listed below.

Expected adverse events

The treatments provided to both intervention arms are widely available within the NHS, used in standard care and considered to be safe. Known adverse events (listed in the table below) are related to their respective trial interventions. These events are secondary outcomes and will be collected as part of the eCRF. The number of occurrences of expected AEs and SAEs will be regularly reviewed throughout the trial by the TMG and the DMC.

Expected AE	Expected SAE
Related to Cochlear Implantation (intervention arm only)	
Facial nerve stimulation (temporary)	Facial nerve stimulation (chronic)
Patient reported decreased hearing ability or loss of residual acoustic hearing (temporary or permanent)	The inability to use the implant or a hearing aid in that ear
Vestibular dysfunction (temporary)	Vestibular dysfunction (chronic)
Perception of non-auditory sensations (temporary or permanent)	Infection requiring hospitalisation (e.g., meningitis and the need for vaccination)
New onset or exacerbation of pre-existing tinnitus	Any surgical complication that requires hospitalisation
Altered taste	Need for revision surgery, reimplantation or explantation
Facial weakness	Subdural injury
Acute otitis media or any other infection treated by oral antibiotics	Chronic pain in or around the implant site or hearing aid
Perilymph fistula	

Expected AE	Expected SAE
Concurrent cerebrospinal fluid (CSF) leakage	
Subcutaneous haematoma	
Unsatisfactory device insertion (e.g., misplacement of electrode array, incomplete electrode insertion, tip fold-over)	
Failure of component parts	
Related to Hearing Aids (intervention and comparator arms)	
Ear infection	None
Exacerbation of eczema	

Serious Adverse Events

A Serious Adverse Event (SAE) is any adverse event occurring following trial mandated procedures that results in any of the following outcomes:

1. Death
2. A life-threatening adverse event
3. Inpatient hospitalisation or prolongation of existing hospitalisation
4. A disability / incapacity
5. A congenital anomaly in the offspring of a participant

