A distinction is drawn between serious and severe AEs. Severity is a measure of intensity whereas seriousness is defined using the criteria above. Hence, a severe AE need not necessarily be serious.

Important medical events that may not result in death, be life-threatening, or require hospitalisation may be considered a SAE when, based upon appropriate medical judgment, they may jeopardize the patient or participant and may require medical or surgical intervention to prevent one of the outcomes listed in this definition.

Events deemed by the investigator to be related to COVID-19 infection will not be reportable.

If an adverse event, *not listed as expected AEs above*, meets, or potentially meets, the SAE criteria it will be assessed for seriousness, and causality.

Causality

Not related or improbable: a clinical event including laboratory test abnormality with temporal relationship to trial device which makes a causal relationship incompatible or for which other treatment, drugs, chemicals or disease provide a plausible explanation. This will be counted as “unrelated” for notification purposes.

Possible: a clinical event, including laboratory test abnormality, with temporal relationship to trial device which makes a causal relationship a reasonable possibility, but which could also be explained by other treatments, devices, drugs, chemicals or concurrent disease. This will be counted as “related” for notification purposes.

Probable: a clinical event, including laboratory test abnormality, with temporal relationship to trial device which makes a causal relationship a reasonable possibility, and is unlikely to be due to other treatments, devices, drugs, chemicals or concurrent disease. This will be counted as “related” for notification purposes.

Definite: a clinical event, including laboratory test abnormality, with temporal relationship to trial device which makes a causal relationship a reasonable possibility, and which can definitely not be attributed to other causes. This will be counted as “related” for notification purposes.

Recording and Reporting of Adverse Events

The below section **does not pertain to** expected AEs and SAEs (included in table of expected events above) which do not require expedited reporting with a trial SAE form. These events are secondary outcomes recorded in medical notes and collected as part of the eCRF, that will be routinely centrally monitored and reported.

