All adverse events (AEs) will be recorded as they are reported whether spontaneously volunteered or in response to questioning about wellbeing at trial visits. The questioning about AEs will cover the current visit as well as the period of time between the previous and the current visit. A note of any concomitant medication will also be made, where available, so that a full assessment of the AE can be made.

Abnormal test results that are deemed clinically significant by the investigator and that lead to a change or temporary or permanent discontinuation in the use of the device or require intervention or diagnostic evaluation to assess the risk to the subject will be recorded as adverse events and instigate further investigation and follow up as appropriate.

All AEs and SAEs will be documented in the subject’s medical records. As both trial interventions are well established and have extensive safety profiles already available, only related, or suspected to be related, SAEs will be documented on the eCRF.

For related, or suspected to be related, events, participants should be followed up until resolution or stabilisation of the event. Follow-up information should ideally be provided on a new SAE form.

Participants will be asked to contact the trial site immediately in the event of any SAEs. The Chief Investigator or nominated deputy shall be informed immediately of any related, or suspected to be related, serious events and shall determine seriousness and relationship in conjunction with any treating medical practitioners.

SAEs will be recorded and reported to the REC and Sponsor as part of the annual progress reports.

SAEs will be reported within the statutory timeframes to the REC as stated below. The Chief Investigator will be responsible for all adverse event reporting.

The NCTU will also notify the trial funder by email from the Chief Investigator to [name] [name], Global Head of Clinical Affairs, Cochlear™ Ltd, [contact] and [name], Clinical Portfolio Manager, Cochlear™ Ltd, [contact] of any serious adverse events at the time of regulatory reporting.

The funder will notify the University by email to [contact] (cc to [contact]) of any reportable events involving devices (Cochlear™ or GN Hearing UK) at the time of reporting to the MHRA, or any other relevant regulatory authorities of any new information which becomes available to them as device manufacturers which could affect the safety of trial participants.

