SAE Reporting Procedure for Unexpected SAEs – At Site

On becoming aware that a participant has experienced an SAE, the Investigator (or delegate) must complete, date and sign an SAE Form. The form should arrive at the NCTU as soon as possible and no later than **24 hours** after first becoming aware of the event:

To report an SAE, email the SAE Form to: [contact]

On receipt, NCTU will allocate each SAE a unique reference number which will be forwarded to the site as proof of receipt. If confirmation of receipt is not received within 1 working day, the site will contact the NCTU. The SAE reference number should be quoted on all correspondence and follow-up reports regarding the SAE and filed with the actual SAE in the ISF.

For SAE forms completed by someone other than the local PI, the Investigator will be required to countersign the original SAE Form to confirm agreement with the causality and severity assessments. For sites where the PI is an audiologist, the responsibility for causality assessment and sign off of SAEs will be delegated to the lead surgeon at site. The form should be returned to NCTU and a copy kept in the ISF.

Investigators should also report SAEs to their own Trust in accordance with local practice.

SAE Reporting Procedure for Unexpected SAE – NCTU

On receipt, NCTU will allocate each SAE a unique reference number which will be forwarded to the site as proof of receipt within 1 working day. The SAE reference number will be quoted on all correspondence and follow-up reports regarding the SAE and filed with the SAE form in the TMF.

On receipt of an SAE Form, seriousness and causality will be determined independently by the Chief Investigator, or their delegate, responsible for determining causality assessments. The Chief Investigator's delegate will review all SAEs reported by the Chief Investigator's host site. An SAE judged by the Investigator, Chief Investigator or their delegate to have a reasonable causal relationship with the trial treatment will be regarded as a related SAE. The Chief Investigator (or their delegate) will also assess all related SAEs for expectedness. If the serious event is unexpected (i.e., is not defined in the protocol as an expected event) it will be classified as an unexpected and related SAE.

SAEs

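### The COVID-19 reporting exemption has no exception for events possibly related to surgery, device or trial procedures, and conflicts with the protocol's own causality and SAE-form rules

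*Protocol*

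**What the plan says.** In the Protocol's Adverse Events chapter, under Serious Adverse Events: "Events deemed by the investigator to be related to COVID-19 infection will not be reportable". No limit is set by seriousness, time since surgery, confirmation of infection, or possible contribution of surgery or device. The rules it meets are these.

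- **Causality.** An event graded 'Possible' has a link to the trial device that is a reasonable possibility but has competing explanations, concurrent disease among them. It counts as related for notification.
- **Recording and Reporting of Adverse Events.** Every AE and SAE goes into the medical records, but "only related, or suspected to be related, SAEs will be documented on the eCRF". Listed expected events are collected on the eCRF by a separate route, without an SAE form.
- **Expected adverse events.** The expected SAEs of implantation include "Infection requiring hospitalisation (e.g., meningitis and the need for vaccination") and surgical complications that lead to admission.
- **SAE Reporting Procedure (site and NCTU).** The site must complete a form within 24 hours of learning of an SAE. Receipt of the form starts an independent causality assessment by the Chief Investigator or a delegate. If either the site or the central assessor finds a reasonable causal link, the SAE is treated as related.
- **Blinding.** "Participants, clinicians and treating staff cannot be blinded to the treatment allocation due to the requirement for some participants to undergo a surgical procedure". Where the local PI is an audiologist, "the responsibility for causality assessment and sign off of SAEs will be delegated to the lead surgeon at site".
- **Trial Configuration.** The intervention is "Unilateral cochlear implantation and offer of a new acoustic HA or optimisation of current HA in the contralateral ear"; the comparator is "Offer of new bilateral acoustic HAs or optimisation of current HAs".

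**The concern.** The exemption turns on one question, whether the investigator relates the event to COVID-19. It does not ask whether trial treatment may also have played a part. A participant admitted with COVID-19 soon after implantation could have an event with both explanations. The causality scale keeps such an event in; the exemption takes it out. Nothing says which prevails.

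Safety of implantation and of hearing aids is a stated secondary objective. The safety summary is to show expected AEs and SAEs and unexpected related SAEs, and the DMC sees outcome data and reported SAEs. An event exempted at site would not enter the second of those categories, and the judgement that exempted it would be made by someone who knows the allocation, with no second look.

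**Working it through.** **What the exemption adds, by type of event**

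1. *COVID-19 alone, no plausible link to trial treatment.* The causality scale puts this in its lowest grade, counted as unrelated. Recording and Reporting already keeps it off the eCRF. The exemption saves the site an SAE form and leaves the trial's safety data unchanged.
2. *COVID-19 with a possible contribution from surgery, device or trial procedure, not a listed event.* Without the exemption, the site completes a form, the central assessor reviews causality, a 'Possible' grade makes it related, and it appears in the safety summary. Read literally, the exemption means no form, hence no central review and no entry.
3. *Infection leading to admission after implantation that may fit the expected-event table.* The table sends it to the eCRF as a secondary outcome. The exemption calls it not reportable. The text does not say whether that covers eCRF collection or only SAE-form reporting.

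The added effect on the safety data is therefore confined to type 2 and, depending on the reading, type 3.

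**Why the missing review matters for type 2.** Ordinarily either the site or the central assessor can classify an SAE as related, so a site's view that an event is unrelated can be overturned. The exemption operates before the form exists, so that second opinion is never given.

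**Scale**

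The denominator is the planned 65 per arm (Sample size and justification). That figure reproduces. With a difference of 15, SD 24, two-sided 5% and 90% power, the normal approximation gives 2 × (1.960 + 1.282)² × 24² / 15² = 53.8, so 54; the t-test version gives 54.8, so 55. Allowing for 15% loss, 55 / 0.85 = 64.7, so 65 per arm and 130 in total.

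- One event: 1/65 = 1.5 percentage points.
- Exact 95% confidence interval with 0 of 65: 0% to 5.5%. With 1 of 65: 0.04% to 8.3%.

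The Protocol gives no rate for COVID-19-attributed events. Under assumed risks p per implant-arm participant, the expected number is 65p and the chance of at least one is 1 − (1 − p)^65:

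| Assumed p | Expected number | Chance of at least one |
|---|---|---|
| 1% | 0.65 | 48% |
| 2% | 1.3 | 73% |
| 5% | 3.25 | 96% |

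These are illustrations for any COVID-19-attributed event. Only the subset of mixed or uncertain cause is at issue, so the relevant numbers are smaller by an unknown factor.

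**The case against.** The strongest reply is that not reportable does not mean not recorded. The Protocol itself separates the two for expected events, which need no expedited form yet are collected on the eCRF. On that reading, type 3 events are kept. This is a fair reading, but the sentence does not state it, and it does not help type 2 events, whose only route into the safety summary runs through an SAE form.

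Second, the lowest causality grade covers events that another disease plausibly explains, so many COVID-19 events would be unrelated anyway. That stands, and it is why the affected group is small. It does not settle the boundary cases, which the 'Possible' grade is there to catch.

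Third, other safeguards exist: events stay in the medical notes, sites report SAEs to their own Trust, and the ethics committee is told at once of any significant safety issue. These stand as protection for participants. They do not put the event into the trial's safety summary.

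A reader might go further and infer three things that the documents do not support.

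- *That the rule can only lower the implant-arm count.* Comparator participants also attend sites for fitting and follow-up, and some may be implanted: the eligibility section provides for further data collection "if a participant had a CI procedure prior to the end of the 9 month period post treatment activation". Safety is summarised by treatment received. Mainly is justified; only is not.
- *That the rule hides serious post-operative harm, or that investigators would attribute complications away.* The events are documented in the notes, and nothing indicates misattribution. Unblinded site judgement applies to every event in this open trial; what is particular here is that the judgement goes unreviewed.
- *That one omitted event would change the safety conclusion.* Safety is reported descriptively, with no threshold. The 1.5 points is simply the weight of any single event.

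**Conclusion.** The point holds as a conflict between rules. The exemption is unqualified, contradicts the 'Possible' grade in the Causality section and the site's duty to complete an SAE form, and leaves collection of a listed infection unclear. Its added effect is on COVID-19 events of mixed or uncertain cause, mainly in participants who have implant surgery, and those events escape central causality review.

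The size is small: few events are expected, each worth 1.5 percentage points among 65. This rests on taking the sentence literally and on the planned arm size; no event rate is available. It is a cheap improvement, not a threat to the trial's conclusions.

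**What to change.** Amend the sentence and reconcile it with the neighbouring sections:

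- limit the exemption to COVID-19 events judged unrelated to trial procedures and devices;
- handle COVID-19 SAEs that are related or possibly related as any other SAE, including central causality review, and include them in the safety summary;
- state that events listed in the expected-event table are still collected on the eCRF.

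This keeps the exemption's evident purpose, which is to spare sites forms for background COVID-19 illness, and alters reporting only. The cost is a short protocol amendment and a handful of extra SAE forms at most.

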The number of participants experiencing at least one AE or SAE will be summarised using descriptive statistics. The total number and type of AEs and SAEs will also be summarised, overall and by event.

Procedures for missing, unused and spurious data

It is planned that several strategies to investigate the effect of missing primary outcome data will be undertaken as sensitivity analyses, including the use of multiple imputation with chained equations and minimisation variables as covariates. More information on methods will be included within the SAP.

Definition of populations analysed

Full analysis set, including safety: All randomised participants for whom at least one post-baseline assessment is available.

There will not be a per-protocol dataset.

ADVERSE EVENTS

Reporting requirements

The collection and reporting of Adverse Events (AEs) will be in accordance with the UK Policy Framework for Health and Social Care Research 2017 and the requirements of the Research Ethics Committee (REC). Definitions of different types of AEs are listed in the table of abbreviations and definitions.

Reporting Period

Trial related AEs will be collected from time of randomisation (baseline visit) until the collection of the primary outcome (9 months post-treatment onset).

Definitions

Adverse Events

An **adverse event** is any unfavourable and unintended sign, symptom, syndrome or illness that develops or worsens during the period of observation in the trial.

An AE does include a / an:

1. exacerbation of a pre-existing illness.
2. increase in frequency or intensity of a pre-existing episodic event or condition.
3. condition detected or diagnosed after medicinal product/device administration even though it may have been present prior to the start of the trial.
4. continuous persistent disease or symptoms present at baseline that worsen following the start of the trial.

An AE does not include a / an:

1. medical or surgical procedure (e.g., surgery, endoscopy, tooth extraction, transfusion); but the condition that led to the procedure is an AE.
2. pre-existing disease or conditions present or detected at the start of the trial that did not worsen.
3. situations where an untoward medical occurrence has not occurred (e.g., hospitalisations for cosmetic elective surgery, social and / or convenience admissions).

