. Unexpected serious adverse events related to the trial intervention will be reported within the timeframes to the REC as stated below. The Chief Investigator shall be responsible for all adverse event reporting.

A serious adverse event that is unexpected in its severity and seriousness *and* deemed directly related to or suspected to be related to the trial treatment shall be reported to the ethics committee that gave a favourable opinion as stated below.

The event shall be reported immediately of knowledge of its occurrence to the Chief Investigator or their delegate.

The Chief Investigator (or their delegate) will:

- Assess the event for seriousness, expectedness and relatedness to the trial intervention.
- Take appropriate medical action, which may include halting the trial and inform the Sponsor of such action.

- If the event is deemed related to the trial treatment shall inform the REC within 7 days of knowledge of the event.
- Shall, within a further 8 days send any follow-up information and reports to the REC.
- Make any amendments as required to the trial protocol and inform the REC as required.

Reporting to the Research Ethics Committee

Unexpected and Related Serious Adverse Events

NCTU will support the Chief Investigator to ensure that the reporting for all events categorised as unexpected and related SAEs to the REC will be completed within 15 days.

Adverse Events

The REC will be notified immediately if a significant safety issue is identified during the trial. However, reporting of adverse events that are not deemed serious is not required for this trial.

Investigators

Details of all unexpected and related SAEs and any other safety issues which arises during the trial will be reported to PIs. A copy of any such correspondence should be filed in the ISF.

Data Monitoring Committee

The independent DMC will review outcome data at regular intervals throughout the trial, in addition to reported SAEs.

ETHICAL AND REGULATORY ASPECTS

ETHICS COMMITTEE AND REGULATORY APPROVALS

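### A listed expected AE that turns out serious has no stated route to seriousness assessment, and two sections of the protocol test expectedness differently

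*Protocol*

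**What the plan says.** All references are to the protocol.

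- **Definitions, Adverse Events.** Item 6 of what an AE does not include is an "expected AE as listed below". Item 4, on the disease under study, makes an exception for cases worse than expected. Item 6 makes none.
- **Expected adverse events.** The text directly after item 6 reads "Known adverse events (listed in the table below) are related to their respective trial interventions". It continues "These events are secondary outcomes and will be collected as part of the eCRF", and adds "The number of occurrences of expected AEs and SAEs will be regularly reviewed throughout the trial by the TMG and the DMC". The table has an Expected AE column and an Expected SAE column. For hearing aids the Expected SAE entry is None.
- **Serious Adverse Events.** An SAE is defined as an adverse event with one of five outcomes, including inpatient hospitalisation and disability or incapacity. Important medical events may also qualify on medical judgement. An event off the expected-AE list that "meets, or potentially meets, the SAE criteria it will be assessed for seriousness, and causality".
- **Recording and Reporting of Adverse Events.** This section says that it does not apply to listed AEs and SAEs. They need no expedited SAE form and are captured in the eCRF, monitored centrally and reported.
- **SAE Reporting Procedure for Unexpected SAE – NCTU.** "If the serious event is unexpected (i.e., is not defined in the protocol as an expected event"), it becomes an unexpected and related SAE.
- **SAEs** (the subsection that follows). The event to be sent to the ethics committee is "A serious adverse event that is unexpected in its severity and seriousness" and related to treatment.
- **Assessment of safety.** "The number of participants experiencing at least one AE or SAE will be summarised using descriptive statistics".

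**The concern.** A list of expected events normally settles one question only: whether a serious, related event is unexpected. Here it also settles whether the event is an AE at all and whether anyone asks if it is serious. A harm on the list can then be worse than its row implies without any rule that moves it up.

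Two things are at stake. The first is safety oversight: such a case is not sent for the seriousness and causality assessment that an unlisted event would get. The second is the safety comparison under secondary objective c, because the serious/non-serious split depends on how the table is laid out as well as on what happened to the participant. The exemption relies on established safety profiles. Yet the background section says that the balance of risk and benefit in this population, which has more residual hearing, still lacks high-quality evidence.

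**Working it through.** No figure in the protocol is in dispute, so the check is to lay the rules side by side and follow individual events through them.

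**Step 1. Count the table.** Expected AEs: 13 implant-related and 2 hearing-aid-related, 13 + 2 = 15. Expected SAEs: 8 implant-related and 0 hearing-aid-related.

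**Step 2. Definition.** Item 6 says that the 15 expected AEs are not AEs. The next subsection calls them known adverse events. The SAE definition starts from an adverse event, so on item 6 a listed expected AE could never be an SAE. Item 6 names expected AEs only; the 8 Expected SAE rows are not excluded.

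**Step 3. Which expected AEs can become serious without matching a row?** The table already handles several:

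- Facial nerve stimulation and vestibular dysfunction are split into temporary (AE) and chronic (SAE).
- Infection is split into treated with oral antibiotics (AE) and hospitalised (SAE).
- Catch-all SAE rows cover surgical complications needing admission, and revision, reimplantation or explantation.

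Facial weakness, altered taste, perilymph fistula, CSF leakage and haematoma carry no severity or duration limit and have no serious counterpart of their own. They reach the SAE column only through the catch-all rows.

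**Step 4. Follow four cases.**

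| Case | SAE criterion met | Expected SAE row matched | Result under the text |
|---|---|---|---|
| Infection after implantation, admitted | Hospitalisation | Yes | Recorded as an expected SAE |
| Facial weakness, lasting and disabling, no admission or revision | Disability | None | On the AE list, so not assessed; counted as a non-serious expected AE |
| Hearing-aid ear infection in the comparator arm, admitted | Hospitalisation | None (hearing-aid entry is None; the infection row sits under the implant heading, intervention arm only) | As above |
| Surgical complication of implantation, admitted, then fatal | Death | Yes | Expected by list membership; arguably unexpected in severity |

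Cases 2 and 3 show the gap. Cases 1 and 3 show that an infection needing admission can count as serious in one arm and non-serious in the other.

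**Step 5. Expectedness.** Case 4 shows the conflict. The NCTU procedure asks whether the event is defined in the protocol as expected; it is, so it is not an unexpected SAE. The SAEs subsection asks whether it is unexpected in severity and seriousness; a death could be. The reporting section also places listed events outside its scope, so case 4 need not reach the SAE form or the Chief Investigator's assessment, where a severity test would be applied.

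**Step 6. Counts.** The participant counts in Assessment of safety use the bare terms AE and SAE. Item 6 would take listed expected AEs out of the first. The preceding paragraph of that section, and Safety outcomes, both say that numbers of expected AEs and SAEs will be summarised. The count is therefore ambiguous as defined, while the stated intention is to include them.

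**The case against.** The strongest reply is that item 6 only directs listed events into a separate eCRF pathway. They are secondary outcomes, go to the TMG and DMC, are monitored centrally, and are named in the planned summaries. Apart from them, only related or suspected-related SAEs go on the eCRF. An AE count without the listed events would therefore have almost no non-serious content, and nobody would intend that. A reader might infer from item 6 that the AE totals will leave out every known complication; these sections do not support that inference. The reply stands on this.

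The table also classifies most serious forms in advance. Permanent loss of residual hearing is a weak example of a gap: it is deliberately listed as temporary or permanent, next to an Expected SAE row for being unable to use the implant or a hearing aid in that ear. A life-threatening CSF leak or perilymph fistula would very plausibly lead to admission or revision and so match a catch-all row. This stands too and narrows the gap, but it leaves cases 2 and 3 open.

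Finally, exempting expected SAEs from expedited reporting is an explicit choice with a stated reason, and immediate ethics committee notification of a significant safety issue remains. A reader might treat the exemption itself as a fault; it is a design choice. It does not explain why there are two expectedness tests, or why a listed AE that may be serious is not assessed.

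**Conclusion.** The point holds in three parts: item 6 contradicts the text around it; the restriction on seriousness and causality assessment leaves some serious listed AEs with no stated route; and the two expectedness tests can classify the same event differently. The consequence is misclassification and missed escalation, with events still recorded.

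The affected set is the part of the 15 expected AEs that meets an SAE criterion but none of the 8 Expected SAE rows. It is probably small in the implant arm, where the catch-all rows apply. For the 2 hearing-aid events there is no Expected SAE row at all.

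No rate can be given, because the protocol states no event frequencies. A reader might take one event among the 65 randomised to implantation, 1/65 = 1.5 percentage points, as the size of the error. That is only a scale: the event is hypothetical, and safety is summarised by treatment received, so 65 need not be the denominator.

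The verdict assumes that sites and the trials unit apply the text as written. Working documents not shown may already send such cases for review, but the protocol would still contradict itself. The change should be made, since it bears on participant safety and costs little.

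**What to change.** 1. Delete item 6, or reword it so that listed events are AEs recorded through the eCRF pathway.
2. Under Serious Adverse Events, add that a listed expected AE that meets or may meet an SAE criterion is also assessed for seriousness and causality, in both arms.
3. Reconcile the scope statement in Recording and Reporting of Adverse Events, the NCTU procedure and the SAEs subsection into one expectedness rule that takes account of severity and outcome as well as list membership.
4. In Assessment of safety, state that the AE and SAE counts include listed events.

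The routine exemption of expected SAEs from expedited reporting may stay. The cost is a protocol amendment limited to wording, and a few more SAE assessments.
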